Management of infusion reactions: refer to institutional policy; see section 6.4 for additional guidance. Steroids should be avoided as a routine premedication due to possible interference with the efficacy of the study agents. Pre-medications are not required but are allowed for patients with previous infusion reaction.

Treatment Period.

The treatment period of the induction phase is Day 1-84 (12 weeks).

The treatment period of the maintenance phase is from Day 85 to 337 (36 weeks). Day

337 is the last protocol-directed infusion of nivolumab (see below) and the last dose of troriluzole.

Adherence/Compliance. At the visit, each subject will be given a bottle containing capsules of study drug. The participant will be requested to maintain a medication diary of each dose of medication. The medication diary will be returned to clinic staff at the end of each cycle. Unused study medication will be returned to the research pharmacy. At the end of each cycle of treatment, the actual amount of unused drug will be compared to the amount taken as recorded on the subject's medication diary. The desired level of compliance is >75%. If a subject is below that threshold, the treating investigator should assess barriers to compliance and address any correctable barriers (e.g. antiemetic therapy). Patients who cannot maintain this level of compliance may be removed from the study at the discretion of the treating investigator.

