5.8 Criteria for Taking a Participant Off Protocol Therapy

Safety Run-In and Randomized Treatment:

Duration of therapy will depend on individual response, evidence of disease progression and tolerance. In the absence of treatment delays due to adverse event(s), treatment may continue until Day 337 or until one of the following criteria applies:

- Disease progression, with the following exceptions:
 - To allow for the possibility of pseudoprogression, investigators may continue to treat a patient beyond progression until the next assessment if the investigator believes the patient is clinically benefitting (must document in progress note). If PD is confirmed on a subsequent scan, therapy must be discontinued.
 - Investigators may continue to treat a patient beyond progression if the progressing lesion(s) can be addressed with brain-directed SRT (See Section 5.6). *NOTE:* To continue on study after SRT, the subject must have at least 1 non-irradiated target lesion and/or non-target lesion in the brain or body.
- Intercurrent illness that prevents further administration of treatment
- Unacceptable adverse event(s)
- Participant demonstrates an inability or unwillingness to comply with the oral medication regimen and/or documentation requirements
- Participant decides to withdraw from the protocol therapy
- General or specific changes in the participant's condition render the participant unacceptable for further treatment in the judgment of the treating investigator

Participants will be removed from the protocol therapy when any of these criteria apply. The reason for removal from protocol therapy, and the date the participant was removed, must be documented in the case report form (CRF). Alternative care options will be discussed with the participant.

When a participant is removed from protocol therapy and/or is off of the study, the participant's status must be updated in OnCore in accordance with [REGIST-OP-1](#).

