6.4 Ipilimumab and Nivolumab

Dose modifications for nivolumab in combination with ipilimumab by adverse event type are detailed in Table 6.1. No dose reductions are allowed. General considerations for holding the dose(s) are as follows.

For the initial induction period, patients with Grade 2 or 3 events requiring discontinuation of treatment with the combination may consider continuing treatment with single agent nivolumab when the event resolves to grade 0-1 (or baseline, when baseline grade is >1). If induction cycles (Ipilimumab + Nivolumab) are held, they will be omitted, not delayed.

Nivolumab monotherapy may be continued at treating investigator discretion if there is evidence of clinical benefit. In this event, patient will continue nivolumab until AE is resolved and ipilimumab may be re-started or if ipilimumab is permanently discontinued (in congruence with guidelines in table below), then patient will continue nivolumab alone until cycles are completed. At completion of 4 dose of combination IPI + NIVO, patient may continue on nivolumab alone, as per protocol. If ipilimumab is permanently discontinued prior to receipt of 4 doses, nivolumab dosing should remain at the induction dosing (refer to Section 5) until completion of induction, and should then switch to maintenance dosing (refer to Section 5).

Example: Following IPI + NIVO treatment on Day 22, there is a grade 3 AE and Day 43 is held. The patient is treated with steroids and the grade 3 AE resolves quickly. The patient has been tapered down to a steroid dose of prednisone 5 mg po daily by Day 64 and the investigator wishes to continue protocol therapy with nivolumab monotherapy. The patient will receive nivolumab (induction dosing) on Day 64, and then continue as per the Study Calendar.

In addition to the AEs identified in the table below, ipilimumab and nivolumab dose should be delayed for any AE, laboratory abnormality or inter-current illness which, in the judgment of the treating investigator, warrants delaying the dose of study medication.

NOTE: Patients who receive systemic corticosteroids for any reason (including toxicity or management of symptoms brain metastases) must be off corticosteroids or have tapered down to an equivalent dose of prednisone 10 mg/day (dexamethasone \leq 1.5 mg PO daily) or less to continue immune checkpoint therapy.

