Following the Safety Run-in, all participants will be enrolled on the randomized portion of the study.

Primary Endpoint. The primary endpoint of the study is global progression-free survival in patients with melanoma brain metastases who are treated with INT vs. INP. Of particular interest will be PFS at 6 months.

PFS is defined as the time from random assignment to the earlier of death or documented disease progression in the intracranial or extracranial compartments. The follow-up of patients who have neither died nor progressed will be censored at the date of the last follow-up visit.

Secondary Endpoints. The secondary objectives and their associated endpoints evaluate other important clinical outcomes, including overall survival (OS), intracranial response rate (RR) and

PFS, extracranial RR and PFS, and safety (number of participants experiencing adverse events, particularly neurologic events). We will also investigate:

- tolerability (number of induction cycles administered, number of maintenance cycles administered)
- use of corticosteroids for management of symptomatic cerebral edema (number of participants)
- use of corticosteroids for management of immune related adverse events (number of participants who require prednisone ≥ 1 mg/kg or equivalent)
- frequency of clinically-indicated stereotactic radiation therapy to the brain on study (number of patients, number of instances and number of lesions irradiated)
- frequency of clinically-indicated surgical intervention to the brain on study (number of participants)

Planned subgroup analyses according to baseline characteristics:

- Prior anti-PD-1 exposure (yes vs. no – if yes then adjuvant vs. metastatic setting)
- Prior ipilimumab exposure (yes vs. no)
- Age (<65 years vs 65 years or older)
- ECOG (0 vs 1)
- LDH at baseline (normal vs. elevated)
- Number of brain metastases (<3 vs 3 or more)
- Brain-directed stereotactic radiation therapy prior to study entry (yes vs. no)
- Craniotomy prior to study entry (yes vs. no)

Planned subgroup analyses according to on-study events:

- On-study brain-directed stereotactic radiation therapy (yes vs. no)

Exploratory Endpoints:

- associations between BRAF/NRAS mutation status and response endpoints, as well as tissue biomarker profiles between paired tissues from extracranial and intracranial metastases from individual patients, where available

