Adverse events will be summarized for all patients having received one or more doses of study therapy and reported according to CTCAE (Version 5.0). The data for each dose cohort in the dose escalation will be summarized separately as will the safety data from the randomized portion of the trial. The proportions of patients in the randomized trial with grade-3 or higher toxicities will be presented with 90% exact binomial confidence intervals. The incidence of events that are new or worsening from the time of first dose of therapy will be summarized according to system organ class and/or preferred term, severity (based on CTCAE grade), type of adverse event, and relation to study treatment. Deaths reportable as SAEs and non-fatal serious adverse events will be listed by patient and tabulated by primary system organ class, and type of adverse event. Of particular interest are serious neurologic events such as seizure, intracranial hemorrhage, and radiation necrosis.

Tolerability

Drug administration will be summarized for all patients having received one or more doses of study therapy. Tolerability will be described by the number of induction cycles administered, the number of maintenance cycles administered, and the frequency of discontinuation of therapy due to toxicity.

Planned Subgroup Analyses

Pre-specified subgroup analyses according to baseline characteristics will be conducted using PHMC methods and will be based on the statistical interaction of treatment assignment and the characteristic. Statistical inference will be based on the interaction p-value. Forest plots will be used to show the results graphically.

Preplanned sub-analyses will be conducted on patients who received on-study brain-directed stereotactic radiation (“radiation salvage subgroup”). Tumor response in the non-irradiated brain lesions and overall survival will be described.

Preplanned sub-analyses will be conducted on patients who required corticosteroids to treat either cerebral edema or immune-related adverse events (“steroid-treated subgroups”).

Due to the potential for guarantee-time bias in these analyses, a conditional landmark approach will be used to evaluate these data.

Exploratory Analyses

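### The tolerability measures in 13.6 depend on how long patients stay progression-free, so they do not isolate tolerability between arms: maintenance counts favour INT and the crude toxicity-stop frequency disfavours it

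*Combined protocol and SAP*

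**What the plan says.** Section 13.6 (Tolerability) covers every patient who received at least one dose. It names three measures. Two are counts: "Tolerability will be described by the number of induction cycles administered, the number of maintenance cycles administered". The third, which Section 13.6 alone lists under tolerability, is "the frequency of discontinuation of therapy due to toxicity". Sections 1.3 and 13.1 name only the two counts ("tolerability (number of induction cycles administered, number of maintenance cycles administered"). None of these places gives a denominator, a time at risk or a way of handling patients who stop for another reason.

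Section 5.8 sets how long treatment lasts: "treatment may continue until Day 337 or until one of the following criteria applies". Progression is one of those criteria. Treatment past progression is allowed until the next assessment or with brain-directed SRT, but otherwise "If PD is confirmed on a subsequent scan, therapy must be discontinued".

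On induction, Section 6.4 says that when ipilimumab plus nivolumab cycles "are held, they will be omitted, not delayed".

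Safety is a separate paragraph of 13.6: "The proportions of patients in the randomized trial with grade-3 or higher toxicities will be presented with 90% exact binomial confidence intervals", with adverse events also tabulated by severity and relation to treatment. No test, threshold or decision rule is attached to tolerability.

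**The concern.** A patient who progresses stops receiving cycles, whatever the tolerability. The maintenance count is therefore largely a reading of PFS, the primary endpoint on which the arms are expected to differ. If INT works as assumed, its patients receive more maintenance cycles at equal tolerability, and may do so at worse tolerability.

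The crude frequency of toxicity stops is pushed the other way. Patients who stay progression-free longer have more time on drug in which to stop for toxicity, so INT shows more stops at the same underlying risk.

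At stake is a stated secondary objective. With an effective drug and equal toxicity, one planned measure would suggest that INT is better tolerated and the other that it is worse, and the plan gives no way to choose between them.

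**Working it through.** **Inputs.** INP 6-month PFS 0.6, cure fractions 30% (INP) and 50% (INT), hazard ratio 0.557 (Section 13.2). Infusions: four in induction (Days 1, 22, 43, 64) and ten in maintenance (every 28 days from Day 85 to Day 337; Sections 5.3 and 10). Toxicity-stop rates: 27% from the brain-metastasis study and 36% from combination therapy (Section 2.5). A low value of 15% is an assumption.

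**PFS curves.** S(t) = π + (1 − π)exp(−λt), t in months.
- INP: 0.3 + 0.7exp(−6λ) = 0.6 gives λ = ln(0.7/0.3)/6 = 0.1412.
- INT: 0.557 × 0.1412 = 0.0787, so S(6) = 0.5 + 0.5exp(−0.472) = 0.812.

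**The plan's own figure.** The plan gives no number for tolerability, so the check is on the design that supplies the curves. An INT 6-month PFS of exactly 0.80 (hazard ratio 0.603) with two-sided type I error 0.1 needs 89 patients and has 80.3% power at 90, which reproduces the stated 90 and 80%. The printed 0.557 gives 0.812, 81 patients and 83.7% power at 90. The printed ratio is used below; 0.603 barely changes the results (last step).

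**Model.** Toxicity stops occur at a constant hazard h, independent of progression, and treatment ends at progression.
- Expected infusions = sum over infusion days d of S(d)·exp(−hd).
- Crude toxicity stops by Day 337 = ∫ h·exp(−ht)·S(t)dt.
- h is set so that INP's crude stops equal the chosen rate; 27% gives h = 0.046 per month, or 0.046 × 28/30.44 = 0.042 per 28 days.

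**Results at equal toxicity hazards.**

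| INP stop rate | Maintenance infusions, INP vs INT | Crude stops, INP vs INT | INT/INP toxicity hazard at which maintenance counts match |
|---|---|---|---|
| none | 5.8 vs 8.0 | – | – |
| 15% | 5.0 vs 6.8 | 15% vs 19% | 3.1 |
| 27% | 4.4 vs 5.9 | 27% vs 34% | 2.05 |
| 36% | 3.8 vs 5.2 | 36% vs 45% | 1.72 |

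With INT's hazard 1.5 times INP's (27% row), INT still shows more maintenance infusions, 5.1 vs 4.4, while its crude stops are about 46%.

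**Induction.** At 27% and equal hazards the expected count is 3.46 vs 3.66, a shift of 0.20 of 4 cycles.

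**Sensitivity.** Four variants were run at 27%: constant hazard or three times higher in induction, and treatment ending at progression or at the next scheduled scan. Total cycles match at 1.9 to 2.1 times INP's hazard (1.6 to 3.1 over the 15-36% range). INT's crude stops at equal hazards are 30-34%. With hazard ratio 0.603 in place of 0.557 (constant hazard, 27%), maintenance infusions are 4.4 vs 5.8 and match at 2.0.

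**Do the alternatives work?** At 27%, maintenance cycles given over maintenance cycles due before progression are:
- INP: 4.35/5.82 = 0.75.
- INT, equal hazard: 5.89/7.96 = 0.74.
- INT, 1.5 times the hazard: 5.09/7.96 = 0.64.

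This ratio is nearly unaffected by PFS and detects the excess. Toxicity stops per time on treatment recover the 1.5 under a constant hazard. With a threefold induction hazard the pooled rate ratio falls to about 1.44, so the rate should be split by phase. Cumulative incidence with progression and death as competing events is, with everyone followed to Day 337, the same integral as the crude frequency, so it keeps the dependence on PFS.

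**The case against.** The strongest defence is that the two measures sit in one sentence and err in opposite directions. A reader would see more cycles and more toxicity stops together, so an excess in INT is not hidden. A PFS difference never makes both measures favour INT: if INT shortened PFS, its crude stops could look reassuring but its cycle counts would fall. The plan also reports grade 3 or higher proportions, severity and attribution tables and serious events, has a neurotoxicity boundary (13.4), and gives the DSMB twice-yearly review (12.2.1). All of this stands. A reader might infer that a more toxic INT arm would look better tolerated overall, or that the trial could not answer the tolerability question. The documents support neither. Only the cycle counts can flatter INT, and the data for a sound analysis are collected.

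The induction count also has a good defence. Held combination cycles are omitted, so it responds directly to toxicity, and Section 5.5 expects most toxicity in Days 1-84. That stands too and confines the count problem mainly to maintenance.

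A constant hazard is a simplification, since Section 6.6 places the usual onset of immune-related events at 3 to 10 weeks. A front-loaded hazard narrows the crude-frequency gap but does not reverse it.

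What the defence does not supply is a measure of ability to stay on treatment that is comparable between arms. The grade 3 or higher proportions are not adjusted for exposure either. Section 13.6 already guards the radiation and steroid subgroups against guarantee-time bias with a landmark approach; tolerability has no comparable safeguard.

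**Conclusion.** The concern holds for the between-arm comparison. Under the plan's own PFS assumptions and equal toxicity, maintenance infusions differ by about 1.5 (4.4 vs 5.9), and similar counts could conceal roughly a doubling of the toxicity-stop hazard (about 1.7 to 3.1 times for assumed INP stop rates of 36% to 15%). The crude stop frequency overstates INT toxicity by about 3 to 7 percentage points at the 27% calibration. Induction is little affected.

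This is a worthwhile, inexpensive improvement to a descriptive secondary summary. It does not threaten the primary analysis, and it should not be read as a route by which excess toxicity escapes notice. The sizes rest on assumptions that the documents do not state: the hazard's shape, independence of toxicity and progression, no treatment beyond progression (which Sections 5.6 and 5.8 allow in part), no dropout, and the 15% value. If the arms do not differ in PFS, the distortion disappears.

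**What to change.** In 13.6, keep the raw counts as description and add, by arm:
- cycles given divided by cycles scheduled before progression, death or Day 337, separately for induction and maintenance;
- toxicity stops per time on treatment by phase, or the cause-specific hazard ratio INT vs INP with progression and death censored.

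Cumulative incidence with competing events may be shown, labelled as description that still depends on PFS. Bring the wording of 1.3 and 13.1 into line.

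Also state which drug a stop of therapy refers to. Section 6.3 lets checkpoint inhibitors continue when troriluzole is held or discontinued, yet removes from the study a patient who cannot restart troriluzole within six weeks. Those statements must be reconciled before stops can be counted consistently.

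The cost is a few sentences and a little more analysis; Section 5.8 already requires the reason and date off therapy on the case report form. Precision will be modest. With 45 patients per arm, 27% and 34% give about 12 and 15 stops, so the standard error of the log hazard ratio is about √(1/12 + 1/15) = 0.39, and a 90% interval runs a factor of about exp(1.645 × 0.387) = 1.9 either side of the estimate. The cause-specific ratio also compares only patients still on treatment, so it should be read alongside PFS.

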13.7 Reporting and Exclusions

Evaluation of Toxicity

All participants will be evaluable for toxicity from the time of their first treatment.

Evaluation of the Primary Efficacy Endpoint

The analysis of the primary endpoint will be conducted using the intention-to-treat principal, meaning all randomized patients will be evaluated according to the treatment assigned at the time of enrollment.

14. PUBLICATION PLAN

The results should be made public within 24 months of reaching the end of the study. The end of the study is the time point at which the last data items are to be reported, or after the outcome data are sufficiently mature for analysis, as defined in the section on Sample Size, Accrual Rate and Study Duration. If a report is planned to be published in a peer-reviewed journal, then that initial release may be an abstract that meets the requirements of the International Committee of Medical Journal Editors. A full report of the outcomes should be made public no later than three (3) years after the end of the study.

APPENDIX A PERFORMANCE STATUS CRITERIA

ECOG Performance Status Scale		Karnofsky Performance Scale	
Grade	Descriptions	Percent	Description
0	Normal activity. Fully active, able to carry on all pre-disease performance without restriction.	100	Normal, no complaints, no evidence of disease.
		90	Able to carry on normal activity; minor signs or symptoms of disease.
1	Symptoms, but ambulatory. Restricted in physically strenuous activity, but ambulatory and able to carry out work of a light or sedentary nature (e.g. , light housework, office work).	80	Normal activity with effort; some signs or symptoms of disease.
		70	Cares for self, unable to carry on normal activity or to do active work.
2	In bed <50% of the time. Ambulatory and capable of all self-care, but unable to carry out any work activities. Up and about more than 50% of waking hours.	60	Requires occasional assistance, but is able to care for most of his/her needs.
		50	Requires considerable assistance and frequent medical care.
3	In bed >50% of the time. Capable of only limited self-care, confined to bed or chair more than 50% of waking hours.	40	Disabled, requires special care and assistance.
		30	Severely disabled, hospitalization indicated. Death not imminent.
4	100% bedridden. Completely disabled. Cannot carry on any self-care. Totally confined to bed or chair.	20	Very sick, hospitalization indicated. Death not imminent.
		10	Moribund, fatal processes progressing rapidly.
5	Dead.	0	Dead.

APPENDIX B MULTI-CENTER GUIDELINES

DF/HCC Protocol #: Pending

Dana-Farber/Harvard Cancer Center Multi-Center Data and Safety Monitoring Plan

1. INTRODUCTION

The Dana-Farber/Harvard Cancer Center Multi-Center Data and Safety Monitoring Plan (DF/HCC DSMP) outlines the procedures for conducting a DF/HCC Multi-Center research protocol. The DF/HCC DSMP serves as a reference for any sites external to DF/HCC that are participating in a DF/HCC clinical trial.

1.1 Purpose

To establish standards that will ensure that a Dana-Farber/Harvard Cancer Center Multi-Center protocol will comply with Federal Regulations, Health Insurance Portability and Accountability Act (HIPAA) requirements and applicable DF/HCC Policies and Operations.

2. GENERAL ROLES AND RESPONSIBILITIES

For DF/HCC Multi-Center Protocols, the following general responsibilities apply, in addition to those outlined in DF/HCC Policies for Sponsor-Investigators:

2.1 Coordinating Center

The Coordinating Center is the entity that provides administrative support to the DF/HCC Sponsor in order that he/she may fulfill the responsibilities outlined in the protocol document and DSMP, and as specified in applicable regulatory guidelines (i.e. CTEP Multi-Center Guidelines).

The general responsibilities of the Coordinating Center may include but are not limited to:

- Assist in protocol development.
- Maintain FDA and other correspondence, as applicable.
- Review registration materials for eligibility and register participants from Participating Institutions in the DF/HCC clinical trial management system (CTMS).
- Distribute protocol and informed consent document updates to External Sites as needed.
- Oversee the data collection process from External Sites.
- Maintain documentation of Serious Adverse Event (SAE) reports and deviations/violation submitted by External Sites and provide to the DF/HCC Sponsor for timely review and submission to the IRB of record, as necessary.
- Distribute serious adverse events reported to the DF/HCC Sponsor that fall under the reporting requirements for the IRB of record to all External Sites.

- Provide External Sites with information regarding DF/HCC requirements that they will be expected to comply with.
- Carry out plan to monitor External Sites either by on-site or remote monitoring.
- Maintain Regulatory documents of all External Sites which includes but is not limited to the following: local IRB approvals/notifications from all External Sites, confirmation of Federalwide Assurances (FWAs) for all sites, all SAE submissions, Screening Logs for all sites, IRB approved consents for all sites
- Conduct regular communications with all External Sites (conference calls, emails, etc) and maintain documentation all relevant communications.

